## **Aim**

The primary aim of this randomized controlled trial was to investigate the effects of an 8-week home-based physiotherapeutic foot-ankle exercise program using an educational booklet on DPN symptoms and severity. The secondary goal was to investigate the effects of this intervention at 8 and 16 weeks on tactile and vibration sensitivities, foot health and functionality, foot muscle strength, functional balance, plantar pressure, foot-ankle kinematics, and lower limbs kinematics and kinetics during gait.

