## **Methods/Design**

### **Study design and data collection**

This trial is designed as a single-blind, two-parallel arms RCT, wherein patients with DPN will be randomly allocated to either a control group (CG) or an intervention group (IG). This trial protocol follows all recommendations established by SPIRIT (2013) [47], has been approved by a research ethics committee (CAAE: 90331718.4.0000.0065), and was registered at ClinicalTrials.gov on July 2, 2019 (identifier NCT04008745).

Patients in the CG will not receive any specific intervention beyond the usual care, including treatment recommended by the medical team, pharmacological treatment, self-care guidelines, and a weekly telephone call to check on the adherence to care, which will be maintained in both groups [48]. Patients in the IG will perform a foot-related exercise program included in an educational booklet three times/week at home for 8 weeks. After 8 weeks, IG

participants will be encouraged to continue this exercise until the end of the study following the same schedule set in the intervention period. If proven effective, the benefits of the foot-related exercises protocol will be explained and offered to all control participants at the end of the study.

Patients from both groups will be evaluated for all outcomes at baseline (T0), 8 weeks (T8, end of intervention), and 16 weeks (T16, follow-up). All procedures in this study will follow the norms of the Operational Procedure Manual developed specifically for this research. The design and flowchart following the Consolidated Standards of Reporting Trials (CONSORT) guidelines [49] are presented in Fig. 1.

[figure not shown]

Figure 1 - Consolidated Standards of Reporting Trials (CONSORT) flow diagram illustrating the process of FOCA-II.

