### **Statistical Analysis Plan**

The sample size was calculated using the GPower v. 3.1 program [64] based on the following outcomes: MNSI DPN symptoms (primary) and ankle sagittal ROM during gait (secondary). These two outcomes were chosen because they reflect important functional gains for DPN patients. Thus, two sample size calculations were performed, and we selected the one that resulted in the largest number of participants. The effect sizes used for both calculations were based on a study that evaluated the effect of 12 weeks of supervised foot exercise in DM patients [34]. In that study, the improvement in the MNSI symptoms had a medium effect size

(0.52), as did gains in the ankle sagittal ROM during gait (0.46). We chose to use half of the effect size obtained in [34] because the nature of our intervention is home based, whereas Sartor's was face-to-face, which is assumed to be more effective.

The input factors for sample size calculation were a statistical design of F-test with interaction between and within factors with two repeated measures and two study groups, statistical power of 0.80, alpha of 0.05, and effect sizes of 0.26 (MNSI symptoms) and 0.23 (ankle ROM). The resulting sample sizes were 32 and 40 individuals for MNSI and ROM outcomes, respectively. Therefore, we defined our sample size as 40. Assuming a 20% dropout rate during the study, a sample size of 48 patients is needed.

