Inferential statistical analyses will be conducted using intention-to-treat and per protocol analyses. The missing data will be treated by imputation methods depending on the type: missing completely at random, missing at random, or not at random [65]. The per-protocol analysis will include only those patients who complete follow-up in the allocated intervention group. Confirmation of normality (Kolmogorov–Smirnov test), homoscedasticity (Levene test), and imputation of the means for the missing data of variables with normal distribution will be conducted. After that, mixed general linear models of analysis of variance for repeated measures will be used to detect treatment–time interactions, followed by Newman–Keuls post hoc test to obtain group effect (intervention and control), time effect (between T0, T8, and T16), and group–time interaction. Significant differences will be considered at  $\alpha = 5\%$ , but for the description of the effect of the intervention, the effect size (Cohen coefficient) and difference between the means will be calculated with their respective 95% confidence intervals.

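### No primary visit or between-group contrast is declared; pre-specified baseline-adjusted contrasts at T8 and T16 should replace the Newman–Keuls step

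*Combined protocol and SAP*

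**What the plan says.** All references are to the combined protocol and SAP.

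- **Statistical Analysis Plan, analysis paragraph.** A mixed repeated-measures ANOVA is assigned to detect the treatment-by-time interaction, "followed by Newman–Keuls post hoc test to obtain group effect (intervention and control), time effect (between T0, T8, and T16), and group–time interaction". To describe the effect, a Cohen coefficient and the "difference between the means will be calculated with their respective 95% confidence intervals". No visit, contrast, baseline covariate, post hoc error term or gatekeeping rule is given.
- **Aim.** "The primary aim of this randomized controlled trial was to investigate the effects of an 8-week home-based physiotherapeutic foot-ankle exercise program" on symptoms and severity: the eight weeks describe the programme, not an assessment. For the other outcomes the weeks are given: "The secondary goal was to investigate the effects of this intervention at 8 and 16 weeks on tactile and vibration sensitivities" and further measures.
- **Outcomes and measures.** MNSI symptoms and the fuzzy severity score are the two primary outcomes, with no primary visit named.
- **Study design and data collection.** Every outcome is measured at T0, T8 (labelled end of intervention) and T16 (labelled follow-up). After week 8, intervention "participants will be encouraged to continue this exercise until the end of the study following the same schedule".
- **Statistical Analysis Plan, sample size.** The calculation uses "a statistical design of F-test with interaction between and within factors with two repeated measures and two study groups", with "statistical power of 0.80, alpha of 0.05" and effect sizes of 0.26 (MNSI) and 0.23 (ankle ROM). It gives 32 and 40, and 48 after a 20% dropout allowance.

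**The concern.** A significant interaction over three visits shows that the two profiles are not parallel. It does not say at which visit the groups differ, or by how much. The plan leaves that to Newman–Keuls and to mean differences with no visit attached.

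Newman–Keuls compares pairs of cell means. It does not test an interaction or a between-group difference in change, and it makes no use of baseline when it compares the groups at T8. Its result depends on two unstated choices: whether the error term is pooled or within-subject, and whether the step is read only after a significant interaction. Both bear on what is reported for a primary outcome, and as written both could be settled after the data are seen. What is at stake is a defined target and some precision.

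**Working it through.** **Inputs.** From the sample size text: α = 0.05, power 0.80, effect sizes 0.26 and 0.23, two measures, two groups, N = 32 and 40. Assumed, because the documents do not say: 1:1 allocation, 40 completers, compound symmetry, and correlation ρ = 0.5 between visits.

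**1. Reproduce the plan's figures.** For the G*Power within-between interaction with m = 2, λ = f²·N·m/(1−ρ) on (1, N−2) df.
- MNSI: 0.26² × 32 × 2/0.5 = 8.65, power 0.812.
- Ankle ROM: 0.23² × 40 × 2/0.5 = 8.46, power 0.809.

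Both stated sizes follow at ρ = 0.5. With ρ = 0.3 they would be 44 and 54; with ρ = 0.7, 20 and 26. In a 2×2 interaction f = δ/4, so 0.26 corresponds to δ = 4 × 0.26 = 1.04 SD between groups. The test that was sized is a comparison of change from baseline to one later visit.

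**2. MNSI power at N = 40, ρ = 0.5, δ = 1.04 at T8.**

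| Test | λ | df | Power |
|---|---|---|---|
| T8, unadjusted: δ²N/4 | 10.82 | 1, 38 | 0.893 |
| T8, change score: δ²N/[8(1−ρ)] | 10.82 | 1, 38 | 0.893 |
| T8, baseline-adjusted: δ²N/[4(1−ρ²)] | 14.42 | 1, 37 | 0.959 |
| Three-visit interaction, T16 effect kept or lost | 14.42 | 2, 76 | 0.925 |
| Three-visit interaction, T16 effect halved | 10.82 | 2, 76 | 0.831 |

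The interaction rows use λ = N·Σ(d_t − d̄)²/[4(1−ρ)]. For the kept profile (0, 1.04, 1.04) the sum of squares is 0.721, so λ = 40 × 0.721/2 = 14.42. A 20% loss from 48 leaves 38.4; with 38 completers the adjusted power is 0.949.

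**3. Precision at T8.** The 95% half-width is t × √(4/40) = 0.640 SD unadjusted and t × √[(4/40)(1−0.25)] = 0.555 SD adjusted.

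**4. Newman–Keuls at T8.** This was simulated with 20 per arm, six cell means and the effect kept at T16.

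| Error term | Read only after a significant interaction | Read regardless |
|---|---|---|
| Pooled | about 74% | about 78% |
| Within-subject | about 88% | about 94% |

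The 94% is not comparable with the adjusted 96%. Within-subject error leaves out between-subject variance: at ρ = 0.5 it puts the standard error of a group difference at √(1−0.5) = 0.71 of its true value. With no treatment effect, the ungated within-error version separates the arms at T8 or T16 in about 10% of trials. With a steep time trend common to both arms (1 SD per visit) this rises to about 27%. Read only after a significant interaction, these rates fall to about 2% and 4%.

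**5. Sensitivity.**
- *Correlation (MNSI).* At 0.3: adjusted 0.919, change score 0.773, interaction 0.811 / 0.683 / 0.811 (T16 effect kept / halved / lost). At 0.7: adjusted 0.994, change score 0.985, interaction 0.994 / 0.969 / 0.994.
- *0.26 as a Cohen d (ρ = 0.5).* Adjusted 0.152, change score 0.126, interaction 0.121 / 0.102 / 0.121. Gated Newman–Keuls at T8 is 1% (pooled) or 4–5% (within).
- *Growing effect (0.52 SD at T8, 1.04 SD at T16; ρ = 0.5).* Adjusted T8 0.456, interaction 0.831, adjusted T16 0.959. Gated Newman–Keuls at T8 is 14% (pooled) or 38% (within).

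**The case against.** Four objections have force.

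1. **The interaction is validly tested.** The sentence that brings in Newman–Keuls first gives the interaction to the ANOVA. A reader might infer from the later words that the interaction is tested only by a procedure that cannot test it. The text does not support that. What stands is loose wording about what the post hoc step delivers.
2. **Newman–Keuls is not the only route to a T8 answer.** The promised mean differences with CIs are another. What stands is that they have no declared visit or adjustment.
3. **The gap between about 74% and 96% is not the gain from baseline adjustment.** It sets a gated, all-pairs procedure against a single test, and the gate is an assumption because the plan says only that the step follows. Against a plain T8 comparison, adjustment adds 0.959 − 0.893, about 7 percentage points.
4. **T8 is strongly implied.** The programme lasts eight weeks, T8 is labelled end of intervention, and the sample size uses two measures. The fix therefore mostly formalises an existing intention. Implied is still not declared, and the encouragement to keep exercising makes T16 a plausible rival.

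The effect size is also open to doubt. The plan calls 0.52 and 0.46 medium and halves them for a home programme expected to be less effective, yet the reading that reproduces the sample size implies 1.04 SD.

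**Conclusion.** The point holds as a matter of target and efficiency. The interaction test is valid. The plan lacks a declared primary visit, a declared group contrast, and a defined quantity for the promised CIs to describe. That part rests on the text alone and applies to both primary outcomes.

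The size of the gain is conditional. On the stated assumptions, baseline adjustment raises MNSI power at T8 from 89% to 96%, against 83–93% for the interaction test, and narrows the CI half-width by 0.640 − 0.555 = 0.085 SD. At correlation 0.7 the gain over the interaction test nearly vanishes. If 0.26 is a Cohen d, the adjusted contrast, the change score and the interaction test all have only 10–15% power. If the effect grows after week 8, the interaction test outperforms a T8 contrast.

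Two stronger readings should be resisted. Sizing on two measures while analysing three visits might suggest underpowering, but the interaction power (83–93%) lies on both sides of the 89% for the test that was sized, so this is a gap in documentation. The 10% and 27% false-separation rates might suggest that the plan inflates type I error; they arise only if Newman–Keuls is read ungated with within-subject error, and the plan specifies neither. No power figure here covers the fuzzy severity score.

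**What to change.** In the Statistical Analysis Plan section:

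- For each primary outcome (MNSI symptoms and fuzzy severity), name the between-group difference at T8, adjusted for the baseline value, as the primary contrast, by ANCOVA or from a mixed model with baseline as covariate. Make the same contrast at T16 secondary. If the investigators intend another primary visit, they should declare it and use the adjusted contrast there.
- Drop Newman–Keuls. Keep the interaction test if wanted, and state its role. Report within-group changes descriptively.
- Attach the promised mean differences and 95% CIs to these two contrasts.
- In the sample size text, state which test the 40 completers power, the correlation assumed, and whether 0.26 and 0.23 are f or d.

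The cost is SAP wording; baseline is already collected. The price is one degree of freedom, the loss of all-pairs comparisons, and less power than the interaction test if the effect appears late: 46% against 83% in the growing-effect case, where the secondary T16 contrast has 96%. The change does not deal with multiplicity across the two primary outcomes, which needs its own rule.

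### Newman-Keuls is the only planned follow-up to the group-by-time model; over six means it lacks strong familywise control, and the cut-off for one arm difference depends on unrelated means

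*Combined protocol and SAP*

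**What the plan says.** The trial is a "single-blind, two-parallel arms RCT". On visits, the Study design section says: "Patients from both groups will be evaluated for all outcomes at baseline (T0), 8 weeks (T8, end of intervention), and 16 weeks (T16, follow-up". Two arms at three visits make six arm-by-visit means.

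The Statistical Analysis Plan states that "mixed general linear models of analysis of variance for repeated measures will be used to detect treatment–time interactions". The next step in that plan is worded as "followed by Newman–Keuls post hoc test to obtain group effect (intervention and control), time effect (between T0, T8, and T16"; it is also meant to cover how the arms differ in their change over time. The significance level is 5%. As a descriptive summary the plan adds that "the effect size (Cohen coefficient) and difference between the means will be calculated with their respective 95% confidence intervals".

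The plan does not say:
- which set of means Newman-Keuls is applied to;
- whether it is run only after a significant interaction;
- which error term it uses;
- which intervention-control comparison, at which visit, answers the trial's question.

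No other multiplicity adjustment is named.

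**The concern.** The omnibus F-test can say that the arms evolve differently. It cannot say whether the intervention arm differs from control at 8 or at 16 weeks. In this plan only Newman-Keuls turns the model into that statement, so its properties decide which visit-level treatment claims are reported as significant.

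Two properties are unwelcome:
- **Error rate.** Newman-Keuls controls the familywise error when the true null means form one cluster. When they form several separate clusters, each cluster gets its own full 5%. That pattern arises if both arms move together over time, which is plausible because usual care, self-care guidance and weekly calls go to both arms.
- **Cut-off.** The critical value for a pair depends on how many of the other ordered means fall between its two members. The same T8 difference can pass or fail because of where the T0 and T16 means happen to lie.

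At stake are false visit-level claims in some settings and lost power in others.

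**Working it through.** **Inputs from the documents.** Two arms, three visits, alpha 0.05, 48 recruited and 40 evaluable. The sizing is an "F-test with interaction between and within factors with two repeated measures and two study groups" with "statistical power of 0.80, alpha of 0.05, and effect sizes of 0.26 (MNSI symptoms) and 0.23 (ankle ROM" as inputs.

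**Assumed.** 1:1 allocation (24 per arm), correlation between visits 0.3–0.7, variance pooled over cells, and a common shift per visit in SD units. The documents give none of these.

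**1. The plan's own figures.** For the interaction test with two groups, two measurements and assumed correlation 0.5, the noncentrality is f² × N × 2 / (1 − 0.5), with 1 and N − 2 df.
- f = 0.26, N = 32: 0.0676 × 32 × 2 / 0.5 = 8.65, power 0.812.
- f = 0.23, N = 40: 0.0529 × 40 × 2 / 0.5 = 8.46, power 0.809.

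Both stated sample sizes reproduce. They rest on the F-test and not on Newman-Keuls.

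**2. Pairs.** Six means give 6 × 5 / 2 = 15 pairs. Three compare arms at the same visit, six compare visits within an arm, and six compare different arms at different visits.

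**3. Cut-offs.** On the t scale the cut-off is q(0.05; r, df)/√2, where r is the number of ordered means spanned. Pooled df = 6 × 23 = 138.

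| r | 2 | 3 | 4 | 5 | 6 |
|---|---|---|---|---|---|
| cut-off (SE) | 1.98 | 2.37 | 2.60 | 2.76 | 2.89 |

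With the repeated-measures df, (48 − 2) × 2 = 92, the range is 1.99 to 2.91.

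**4. Error rate, not gated on the interaction.** If the visits are well separated and the arms do not differ, each same-visit pair is tested at about 5%. Treating pairs as independent, the limit is 1 − 0.95² = 9.75% for T8 and T16, or 1 − 0.95³ = 14.3% if baseline is counted. Simulated probability of at least one false arm difference:

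| Common shift per visit | T8 or T16 | Baseline also counted |
|---|---|---|
| none to 0.3 SD | 1–3% | about 2% with no shift, at most about 4.6% |
| 0.5 SD | 4–5% | 6–9% |
| 0.8–1.5 SD | 8–10% | 11–14% |

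**5. Error rate, gated on a significant interaction.** A common shift alone gives 1–3% over all three pairs.

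**6. Power.** For a true 0.8 SD difference at T8 only:
- Newman-Keuls, gated: about 50–61%.
- Newman-Keuls, ungated: 57–68%.
- Holm over the T8 and T16 contrasts: 66–70%.

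The advantage is not uniform. Ungated Newman-Keuls has 57–59% power against 67–68% for Holm at common shifts of 0–0.5 SD per visit, but the two are about equal at 0.8 SD.

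**7. The replacement.** Two between-arm contrasts with their own between-patient standard errors and Holm adjustment give a familywise error of 4.3–5.0% (correlation 0 to 0.7). The first-step cut-off is |t| > 2.32 at N = 48 or 2.33 at N = 40, wherever the other means lie. Without adjustment the two contrasts give 8.4–9.8%.

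**The case against.** The strongest defence has five parts.

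- **The six-mean use is inferred.** For the group effect (two means) Newman-Keuls is a single test, and for the time effect (three means) it holds 5%. Only the interaction follow-up can involve six means. This stands as a caveat, but that follow-up is the one that yields visit-level arm differences.
- **The wording may imply a gate.** The model detects interactions and Newman-Keuls follows, post hoc, and the trial is sized on the interaction test. The plan states no gate, but the reading is natural. Under it the common-shift inflation disappears. The variable cut-off and the power loss remain.
- **The shifts that do harm are large.** A shift of 0.8 or 1.5 SD per visit is 1.6 or 3 SD over 16 weeks in both arms, including usual care. Up to 0.3 SD per visit the procedure is conservative. If both arms change by T8 and then plateau, the T8/T16 error is about 2%. This stands.
- **The baseline pair should not count.** A T0 difference between randomized arms supports no treatment claim. This stands, so 9.75% is the relevant limit.
- **The intervals are descriptive.** Newman-Keuls has no matching confidence intervals, but the plan offers its intervals to describe the effect. Unadjusted intervals can disagree with any adjusted test, Holm included. The mismatch carries little weight.

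A reader might also infer error rates of 36–50%, which simulation gives if the within-patient error term is used for between-arm pairs (correlation 0.5–0.7, ungated, baseline counted). The documents do not support this reading, because the plan names no error term. Much of that excess also comes from the error term: Tukey with the same term gives 11% and 23–24%.

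**Conclusion.** The point holds in a limited form and is worth correcting. If applied to six means, Newman-Keuls lacks strong familywise control, and the cut-off for one arm difference varies from about 1.98 to 2.89 SE. That variation needs no assumption about time trends.

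Whether the false-positive rate for T8 and T16 exceeds 5% depends on two unknowns: no gate, and a common shift above roughly 0.5 SD per visit. The rate is then 8–10%, with a limit of 9.75%. With a gate, a common shift alone does not take it above about 3% under the pooled-variance assumptions, and the practical cost is power at T8.

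A reader might infer that the trial runs a 14.3% false-positive rate, or that its main test is invalid. The documents support neither. The first figure needs the baseline pair, no gate and strongly separated visits. The second does not follow, because the interaction F-test and the sample size do not use Newman-Keuls. Nor is inflation after a true T8 effect established at 4–9%. Those figures need a common shift as well and count the baseline pair; without that pair, and with shifts of 0.3–0.8 SD per visit, the rate is 2–5%.

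**What to change.** In the analysis paragraph of the Statistical Analysis Plan, replace the Newman-Keuls test by: *intervention-control comparisons at T8 and T16 from the fitted model, using between-patient standard errors, Holm-adjusted within each outcome, with 95% confidence intervals from the same model*. Do not test the baseline pair, or pairs from different arms at different visits. State whether these comparisons depend on a significant interaction; the Holm adjustment does not need that gate to hold 5% within an outcome.

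The cost is one sentence of wording, with no new data, patients or change to the omnibus model. The downside is that where both arms shift strongly, some post hoc p-values become less favourable than under Newman-Keuls. The adjustment works within one outcome and does not address multiplicity across outcomes.

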### **Outcomes and measures**

Two researchers (Researchers #4 and #5) who are blinded to group allocation will perform all assessments. Participants of both groups will be assessed at baseline (T0), at the end of intervention (T8, 8 weeks after baseline), and at follow-up (T16, 16 weeks after baseline). Table 1 shows the schedule of enrollment, intervention, and assessments according to the SPIRIT guidelines [47].

Table 1 - Schedule of enrollment, intervention, and assessments of the FOCAtrial-II, following SPIRIT guideline

TIMEPOINT	Enrollment	Allocation	Post-allocation	Follow-up	
	T-1	T0	T0	T8	T16
Eligibility screen	X				
Informed consent	X				
Allocation			X		
INTERVENTIONS					
Intervention Group					
Control Group					
ASSESSMENTS					
DPN symptoms		X	X	X	
Fuzzy classification of the DPN severity		X	X	X	
Foot- ankle kinematics and kinetics during gait		X	X	X	
Dynamic plantar pressure distribution during gait		X	X	X	
Tactile sensitivity		X	X	X	
Vibration sensitivity		X	X	X	
Foot health and functionality		X	X	X	
Foot isometric strength		X	X	X	
Functional balance		X	X	X	

An initial anamnesis will be performed to check the eligibility criteria, including clinical, anthropometric, and demographic characteristics of all participants. The classification of DPN severity will be made using the fuzzy score from a web software program [13,53]. Participants with scores equal to or above 2.0, corresponding to mild DPN, will be included in the study. Those who score between 12 and 21 (probable depression) on the Brazilian-Portuguese HADS will not be included [54].

The DPN symptoms and the classification of the DPN severity will be the primary

outcomes. The foot-ankle kinematics and kinetics during gait, plantar pressure distribution during gait, tactile and vibration sensitivities, foot health and functionality, foot strength, and functional balance will be the secondary outcomes.

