The following kinematic variables will be analyzed for the stance phase: (a) sagittal ankle ROM, (b) ankle dorsiflexion at heel strike, (c) ankle plantarflexion at push off, (d) hindfoot to forefoot rotation ROM, (e) transverse plane ROM between first and second metatarsal bones and between second and fifth metatarsal bones, and (f) deformation of the longitudinal medial arch. The ankle kinetic variables to be analyzed are: (a) flexor moment and eccentric power at heel strike and (b) extensor moment and power at approximately 80% of stance phase, corresponding to the propulsion phase.

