### **Plantar pressure distribution during gait**

A  $700 \times 403 \times 15.5$ -mm pressure platform (emed q-100, GmbH, Novel, Munich, Germany) with 6080 sensors (four sensors per  $\text{cm}^2$ ) will be used to acquire plantar pressure data during gait at 100 Hz. Participants will walk barefoot three times over the platform with a self-selected gait speed (same as in the kinematic trials), covering a distance of 4 m. Both feet will be analyzed for each patient. Based on the algorithm by Giacomozi [57], peak pressure, contact area, and pressure-time integral in seven anatomical plantar regions—heel, midfoot, medial forefoot,

medium forefoot, lateral forefoot, hallux, and toes—will be analyzed. This method relies on the integration of a 3D motion capture system (Vicon system), a pressure measurement device (emed q-100), a multi-segment foot model, and an algorithm to identify regions of interest.

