### **Foot health and functionality**

The Brazilian-Portuguese version of the Foot-Health Status Questionnaire (FHSQ-BR), which has been translated and validated by [62], will be used. This questionnaire is divided into three domains, and we will use Domains I and II. These domains are comprised of questions with answer options presented in affirmative sentences and corresponding numbers. Domain I evaluates foot health in four dimensions: foot pain, foot function, footwear, and general foot health. Domain II evaluates the general state of health, also in four dimensions: general health, physical activity, social capacity, and vitality. Domain III collects general demographic data. The domain I and II has a score from 0 to 100 points, where 100 is the best condition and 0 is the worst. The scores will be calculated using the FHSQ software version 1.03 (Care Quest, Australia).

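### About 45 unranked secondary variables are each judged at 5%, with no control across variables and no statement that they are exploratory

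*Combined protocol and SAP*

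**What the plan says.** Outcomes and measures names two primary outcomes (neuropathy symptoms and severity classification) and then lists the rest as one unranked group: gait kinematics and kinetics, followed by "plantar pressure distribution during gait, tactile and vibration sensitivities, foot health and functionality, foot strength, and functional balance will be the secondary outcomes".

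The measurement sections turn that list into individual variables. The gait section has six lettered kinematic items, one of which holds two variables ("transverse plane ROM between first and second metatarsal bones and between second and fifth metatarsal bones"), and four ankle kinetic variables. The pressure section has "peak pressure, contact area, and pressure-time integral in seven anatomical plantar regions". The questionnaire section has two domains of four dimensions each ("Domain I evaluates foot health in four dimensions: foot pain, foot function, footwear, and general foot health", and likewise for general health). Strength, tactile sensitivity, vibration sensitivity and functional reach add the remainder.

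The Statistical Analysis Plan fits repeated-measures models followed by Newman-Keuls comparisons, and states "Significant differences will be considered at" 5%. The same sentence adds that effect sizes and mean differences will be given with 95% confidence intervals. Ankle sagittal range of motion (ROM) is the only secondary variable in the sample-size calculation: "The resulting sample sizes were 32 and 40 individuals for MNSI and ROM outcomes, respectively".

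**The concern.** The label secondary has no consequence in the analysis, because the significance rule is the same for a primary outcome and for any of the pressure variables. No secondary outcome is ranked, no adjustment runs across them, and no sentence limits what may be concluded from them. Newman-Keuls compares means within one variable's model and gives no protection across variables.

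The Aim makes effects on these outcomes at 8 and 16 weeks a stated goal. Under the plan as written, a conclusion that the programme improves gait, plantar pressure or foot health could rest on whichever variables crossed 5%. A reader could not separate those from the number expected by chance.

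**Working it through.** **The plan's own figures.** The inputs in the Statistical Analysis Plan are power 0.80, alpha 0.05, f = 0.26 (symptoms) and f = 0.23 (ankle ROM), for an "F-test with interaction between and within factors with two repeated measures and two study groups". The noncentrality is λ = f² × N × m / (1 − ρ), with m = 2 and 1 and N − 2 degrees of freedom. The plan gives no ρ; I assume 0.5.

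- Symptoms: λ = 0.26² × 32 × 2 / 0.5 = 8.65, power 0.81 at N = 32.
- Ankle ROM: λ = 0.23² × 40 × 2 / 0.5 = 8.46, power 0.81 at N = 40.

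Both stated sizes are reproduced. Power is therefore planned for one secondary variable. The plan states no count of secondary tests and no overall error rate, so those are derived next.

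**Count of secondary variables.**

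| Family | Variables | Count |
|---|---|---|
| Kinematics | five single items, one double | 7 |
| Kinetics | moment and power at two phases | 4 |
| Plantar pressure | 3 measures × 7 regions | 21 |
| Strength | hallux, toes | 2 |
| Foot-health questionnaire | 4 + 4 dimensions | 8 |
| Sensation and balance | tactile, vibration, reach | 3 |
| Total | | 45 |

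Two counting choices are left open:

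- Scoring the questionnaire as two domains gives 45 − 6 = 39.
- Testing each foot separately adds 11 gait, 21 pressure and 2 strength variables (45 + 34 = 79), or 81 if tactile and vibration are also doubled.

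The Aim also mentions lower-limb kinematics and kinetics that the gait section does not itemise, so 45 is a working count and not a ceiling.

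**Expected false positives if the programme has no effect,** with one interaction test per variable:

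- 45 × 0.05 = 2.25. This holds whatever the correlation between tests.
- The tests are two-sided, so half, 45 × 0.025 = 1.125, would favour the programme.
- 39 × 0.05 = 1.95; 79 × 0.05 = 3.95; 81 × 0.05 = 4.05.

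Separate group and time tests, and running both intention-to-treat and per-protocol analyses, are not counted.

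**Chance of at least one false positive among 45.** If independent, 1 − 0.95^45 = 0.90, and in the favourable direction 1 − 0.975^45 = 0.68. The documents give no correlations, so the other rows are assumptions, from simulated equicorrelated normal statistics (200,000 draws each).

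| Common correlation | Mean number | Median | At least one, either direction | At least one favourable |
|---|---|---|---|---|
| 0 | 2.25 | 2 | 90% | 68% |
| 0.5 | 2.25 | 1 | 60% | 30% |
| 0.7 | 2.25 | 0 | 39% | 20% |

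**The case against.** The strongest reply is that the outcomes are openly labelled secondary, that the Aim only proposes to investigate them, and that leaving secondary outcomes unadjusted is a common and defensible choice if they are read as supportive. The plan also does not describe effects by p-value alone: effect sizes and mean differences with 95% intervals are promised in the same sentence as the 5% rule. This stands in part. Estimation is already planned, although the text does not say that the differences are between arms. But the plan never says that the secondary results are only supportive, and the intervals leave the 5% criterion in place.

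The variables are also clearly related: three measures on the same seven regions, ankle ROM beside the dorsiflexion and plantarflexion angles, and eight dimensions of one questionnaire. This stands too, and it limits what can be claimed. A reader might infer that some false significant result is almost certain. The documents do not support that, because the chance runs from 39% to 90% over the correlations considered. A reader might also take 2.25 as what a typical trial would show, or as the number of false benefits. It is a mean (the median is 1 at correlation 0.5 and 0 at 0.7), and only about 1.1 would favour the programme.

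Nor do the documents show that any particular significant secondary estimate will be too large. That is a tendency when small-sample results are selected for significance, and no figure here quantifies it.

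**Conclusion.** The concern holds as a gap in the decision rule. About 45 secondary variables (39 to about 80, depending on scoring and on the handling of the two feet) are each declared significant at 5%, with no control across variables and no exploratory status. Under a global null with one interaction test each, the average is 2.25 false positives, about 1.1 of them in the programme's favour. That average needs no assumption about correlation; the probability of at least one does. Even at an assumed correlation of 0.7 that probability is 39%, nearly eight times the nominal 5%.

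Two stronger readings should be set aside. It would be wrong to say that the plan has no multiple-comparison procedure, since Newman-Keuls is specified within each variable; what is missing is control across variables. Nor does the plan's use of ankle ROM for sizing mean that ROM must be tested only after primary success. There are two primary outcomes and no definition of success, so such a gate could not be run as the plan stands. The point is one the plan should address; it does not undermine the primary comparison.

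**What to change.** Add one paragraph to the Statistical Analysis Plan, before treatment codes are revealed to the statistician:

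- State that the secondary variables are exploratory and supportive.
- Keep the planned estimates with 95% confidence intervals, and specify that the differences are between arms.
- Call a secondary result significant only after Benjamini-Hochberg at 5% within its pre-listed family: kinematics, kinetics, pressure, foot-health questionnaire, strength, and sensation and balance.
- Draw no efficacy conclusion from an unadjusted p-value.
- Fix the questionnaire scoring and the handling of the two feet, so that the count is settled, and report the number of variables tested.

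Ankle sagittal ROM may be named in advance as the one key secondary outcome. It should not be gated on the primary objective unless the plan first defines success for its two primary outcomes and restates the power for ROM. With ρ = 0.5 and N = 40, power is about 0.81 for ROM and 0.89 for symptoms, so gating ROM on symptoms alone gives about 0.81 × 0.89 = 0.72 if the two tests are independent.

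The cost is small: no new data, visits or patients. Some nominal p < 0.05 secondary results can no longer be called significant. Control holds within each family and not across families: with six independent families and no true effects, the chance of some false finding is still 1 − 0.95^6 = 26%. That is acceptable for results labelled exploratory, but the plan should say so.
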